10.2 Secondary Efficacy Analyses

10.2.1 Duration of Confirmed Response

The duration of confirmed response is defined as the time from the date that a response is first reported (which is subsequently confirmed) to the time that progression is first documented plus 1 day.

- For radiographic response, duration of confirmed response is defined as the time from the date that a response (per modified RECIST Version 1.1/PCWG3) is first reported to the time that progression (per modified RECIST Version 1.1 criteria or confirmed bone progression per PCWG3) is first documented. DOR will be summarized separately for patients with confirmed responses per IRR and Investigator.
- For PSA-response, duration of confirmed response (PSA-DOR) is defined as the time from the date that a response (PSA decrease $\geq 50\%$) is first reported to the time that PSA progression (as defined in [Section 10.2.6](#)) is first documented. PSA-DOR will be

summarized separately for patients without measurable disease per IRR and patients without measurable disease per Investigator. PSA-DOR may also be summarized for patients with measurable disease per IRR, patients with measurable disease per Investigator, and for all patients.

Patients without a progression event will be censored at the time of their last assessment (radiographic or PSA, as applicable). The duration of confirmed response will be summarized using Kaplan-Meier methodology. In the case of a low censoring rate, the duration of response may be summarized with descriptive statistics.

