2 OVERALL STUDY DESIGN, OBJECTIVES, AND ENDPOINTS

2.1 Study Objectives and Endpoints

Table 1. Primary, Secondary, and Exploratory Objectives and Endpoints

Primary Objectives	Primary Endpoints

To assess the efficacy of rucaparib based on the response rate in mCRPC patients with HRD who progressed on AR-targeted therapy (abiraterone acetate, enzalutamide, apalutamide, or investigational AR-targeted agent) and taxane-based chemotherapy in the castration-resistant setting
	
A. Cohort A: Confirmed radiographic ORR (as assessed by central independent radiology review [IRR]) using modified RECIST Version 1.1 (ie, CR or PR by IRR assessment and no confirmed progression in bone per PCWG3 by IRR assessment). Analyzed separately for patients with deleterious BRCA1/2 and ATM mutations.
 
B. Cohort B: Confirmed PSA response ($\geq 50\%$ decrease from baseline) as assessed by a local laboratory. Analyzed separately for patients with deleterious BRCA1/2 and ATM mutations.
 
C. Cohort C: Confirmed radiographic ORR (as assessed by central IRR) using either modified RECIST Version 1.1 (if measurable visceral and/or nodal disease is present) or confirmed PSA response ($\geq 50\%$ PSA

	decrease from baseline) (if measurable visceral and/or nodal disease is absent).
Secondary Objectives	Secondary Endpoints
To assess duration of response (DOR)	Time from the date that a response (modified RECIST Version 1.1/PCWG3 criteria or PSA \geq 50%, respectively) is first reported to the time that progression (using modified RECIST Version 1.1/PCWG3 criteria or PSA-progression criteria, respectively) is first documented.
To assess radiographic progression-free survival (rPFS)	Time from first dose of rucaparib to the date of first objective evidence of radiographic progression (soft tissue or bone lesion, using modified RECIST Version 1.1/PCWG3 criteria, respectively) or death due to any cause, whichever comes first
To assess overall survival (OS)	Time from first dose of rucaparib to date of death due to any cause.
To assess clinical benefit rate (CBR)	Proportion of patients with CR, PR, or SD as defined by modified RECIST Version 1.1 and no progression in bone by PCWG3 criteria
To assess PSA response	Confirmed PSA response, defined as having 2 consecutive PSA values (at least 3 weeks apart) that are at least 50% lower than baseline and that occur prior to PSA progression. Similarly, a cut off of at least a 90% reduction will be assessed.

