Quantitative variables will typically be summarized using frequencies and percentages for appropriate categorizations and may also be summarized using descriptive statistics. For variables summarized with descriptive statistics, the following will be presented: N, mean, standard deviation, median, minimum, and maximum. Categorical variables will be presented using frequencies and percentages.

The Kaplan-Meier methodology will be used to summarize time-to-event endpoints. If estimable, the 50th percentile (median) with the 95% confidence interval and range (minimum, maximum) will be summarized. The number of patients with events and the number of censored patients will also be presented.

All data will be used to their maximum possible extent but without any imputations for missing data. Unless otherwise specified, baseline is defined as the last measurement on or prior to the first day of study drug administration.

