10.2.2 Radiographic PFS

rPFS is defined as the time from first dose of rucaparib to the date of first objective evidence of radiographic progression (soft tissue or bone lesion) or death due to any cause, whichever occurs first, plus 1 day. Radiographic disease progression includes confirmed bone disease progression and soft tissue disease progression adjudicated by IRR using the PCWG3 guidelines for bone disease and modified RECIST Version 1.1 for soft tissue disease. Patients without a documented event of progression will be censored on the date of their last adequate tumor assessment (i.e., radiographic assessment) or date of first dose of study drug if no post-baseline tumor assessments have been performed.

Patients who withdraw from treatment prior to radiographic progression will be followed for disease status and survival whenever possible. Only tumor scans (and deaths, for PFS analyses) prior to start of any subsequent anticancer treatment will be included. If a patient discontinues study drug due to a reason other than radiographic PD and subsequently begins another anticancer therapy (ACT) prior to a PFS event, that patient will be censored at the last scan prior to the start of ACT. However, scans/PFS events occurring more than 24 weeks after DC/stop of study drug and more than 24 weeks after their last previous scan but prior to start of subsequent ACT will not be included in the analysis and such patients will be censored at their last scan prior to the end of the 24-week window.

rPFS will be presented by gene mutation for all patients (separately, using IRR and Investigator assessments) and may also be presented by measurable disease status at Baseline.

A sensitivity analysis will be performed in which patients who have discontinued without radiographic progression, but who have had PSA progression, will be treated as having an event at the time of PSA progression.

rPFS will be summarized using Kaplan-Meier methodology and in the case of a low censoring rate it may be summarized with descriptive statistics.

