11 STATISTICAL / ANALYTICAL ISSUES

11.1 Handling of Dropouts or Missing Data

All data will be used to their maximum possible extent but without any imputations for missing data. All time to event analyses include censoring and the rules for deriving the censoring value are described in more detail under each one of the time to event endpoints.

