13 CHANGES IN THE PLANNED ANALYSES

The definition of confirmed PSA responder (primary endpoint for Cohort B) in the protocol has been described in more detail in the SAP. The protocol stated:

Confirmed PSA response is defined as $\geq 50\%$ reduction in PSA from baseline to lowest post-baseline PSA result, with a consecutive assessment conducted at least 3 weeks later. PSA response will be calculated for all patients with PSA values at baseline and at least 1 post-baseline assessment.

This has been updated in the SAP to the following:

Confirmed PSA response is defined as having 2 consecutive PSA values (at least 3 weeks apart) that are at least 50% lower than baseline and that occur prior to PSA progression (as defined in [Section 10.2.6](#)). Per PCWG3, early rises (before 12 weeks following first dose of study drug) in PSA should be ignored when determining PSA response. Confirmed PSA response will be calculated for patients with PSA values at baseline.

The definition of time to PSA progression in the protocol did not contain all the details outlined in the PCWG3 guidelines. The protocol stated:

Time to PSA progression is defined as the time from first dose of rucaparib to the date that a $\geq 25\%$ increase and absolute increase of ≥ 2 ng/mL above the nadir (or baseline value for patients who did not have a decline in PSA) in PSA was measured. The increase must be confirmed by a second consecutive assessment conducted at least 3 weeks later.

This has been updated in the SAP to the following:

Time to PSA progression is defined as the time from first dose of rucaparib to the date that a $\geq 25\%$ increase and absolute increase of ≥ 2 ng/mL above the nadir (or baseline if there was no PSA decline after baseline) in PSA was measured, plus 1 day. The increase must be confirmed by a second consecutive assessment conducted at least 3 weeks later (unless the PSA progression occurred at the last recorded PSA assessment). If confirmed, the date used for time of PSA progression is the earlier of the 2 PSA dates. Additionally, early rises (before 12 weeks following first dose of study drug) are not considered in determining PSA progression.

The clinical benefit rate analysis in the protocol has been described in more detail in the SAP. The protocol stated:

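### Radiographic duration of response censors responders who die without documented progression, and the planned output would not show how many there were

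*SAP*

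**What the plan says.** - **SAP 10.2.1 (DOR).** The clock starts at the first reported response, and the period is defined by "which is subsequently confirmed) to the time that progression is first documented plus 1 day". All other responders fall under "Patients without a progression event will be censored at the time of their last assessment (radiographic or PSA, as applicable". There is no exception for death.
- **SAP Table 1.** DOR runs "to the time that progression (using modified RECIST Version 1.1/PCWG3 criteria or PSA-progression criteria, respectively) is first documented". The protocol synopsis, protocol 11.5.2 and protocol Appendix 2 also stop at progression and do not mention death.
- **SAP 10.2.2 (rPFS).** The event is "radiographic progression (soft tissue or bone lesion) or death due to any cause, whichever occurs first, plus 1 day". Two limits apply. First, "Only tumor scans (and deaths, for PFS analyses) prior to start of any subsequent anticancer treatment will be included". Second, an event is dropped if it falls more than 24 weeks after study drug stops and more than 24 weeks after the previous scan. The censoring sentence in the same section names only the absence of progression. Read alone, it would censor deaths too, against the section's own definition.
- **SAP 11.1.** It says "the rules for deriving the censoring value are described in more detail under each one of the time to event endpoints", so 10.2.1 governs DOR.
- **SAP 3.** The time-to-event output is "The number of patients with events and the number of censored patients will also be presented". No reason for censoring is planned. OS (SAP 10.2.3) is shown by gene group and overall, optionally by measurable disease, but not for responders. No DOR sensitivity analysis counts death.

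**The concern.** Censoring a death at the last scan treats the patient as if his response could still be running. Radiographic DOR will be read beside ORR, as the measure of how long benefit lasts, in a single-arm cohort that may support a regulatory filing. A reader of the planned table could not tell an ongoing response from a responder who had died.

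The protocol leaves room for such deaths:

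- After Week 24, scans are 12 weeks apart.
- Bone progression needs a later confirming scan (protocol Appendix 2).
- Scans continue only until investigator-assessed progression, while DOR is also reported per independent review.

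In these situations a death may follow unrecorded progression, and the censoring would then be informative.

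**Working it through.** **1. The same patient under each rule.** Take a confirmed responder with no documented progression who dies before any new anticancer therapy and inside the 24-week rule. Under the rPFS definition he has an event at death. Under 10.2.1 he is censored at his last scan. In the SAP 3 output he is one of the censored, like a patient still in response.

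**2. Number of responders.** The plan states no DOR figure to reproduce. The responder count comes from Cohort A (BRCA1/2): 0.35 × 83 = 29.05, about 29. That design checks out. P(reject) = Σ (x = 9 to 37) P(X₁ = x) × P(X₂ ≥ 23 − x), with X₁ ~ Bin(37, p) and X₂ ~ Bin(46, p). This gives 0.0487 at p = 0.20 and 0.901 at p = 0.35, against the stated 5% and 90%.

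**3. Underlying median.** Let λ be the constant hazard of a first event, with qλ for death and (1 − q)λ for progression, independent of each other. Counting death, the median is ln 2/λ. Progression-only, it is ln 2/[(1 − q)λ]. The ratio is 1/(1 − q). The documents do not give q, so it is assumed:

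- q = 5%: 1/0.95 = 1.053
- q = 10%: 1/0.90 = 1.111
- q = 20%: 1/0.80 = 1.250

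If a share r of these deaths follows new therapy and would not be counted, the ratio is 1 + (1 − r)q/(1 − q). At r = 0.5 this gives 1.026, 1.056 and 1.125.

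**4. Observed Kaplan-Meier median, 29 responders.** Two sets of simulations used scans at Weeks 8, 16 and 24, then every 12 weeks, with progression dated at the next scan and exponential times to first event after confirmation.

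- Set A (2,500 trials per setting): first response at Week 8 (60%) or 16 (40%), confirmation 4 weeks later, cut-off uniform 26 to 104 weeks after response, median to first event 26/39/52 weeks.
- Set B (2,000 trials per setting): first response at Week 8 (65%) or 16 (35%), confirmation 8 weeks later, follow-up uniform from 0.5 to 1.5 times its mean.

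Share of trials in which the progression-only median is longer:

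| Setting | q = 5% | q = 10% | q = 20% |
|---|---|---|---|
| A, scans on schedule | 20.2/21.0/19.5% | 35.9/41.2/37.4% | 68.2/70.4/61.8% |
| B, median 9 months, mean follow-up 24 months | 25% | 47% | 75% |
| B, median 6 months, mean follow-up 24 months | not run | 42% | 72% |
| B, median 12 months, mean follow-up 24 months | not run | 48% | 77% |
| B, median 9 months, mean follow-up 14 months | not run | 33% | 58% |
| A, ±7-day scan windows | 35.2/28.7/24.3% | 61.5/54.4/44.8% | 88.5/82.0/67.6% |
| A, half the deaths after new therapy | 10.5/10.8/9.9% | 21.7/21.6/18.6% | 42.6/40.8/36.4% |

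The median was shorter under the SAP rule in at most 0.7% of trials in any Set A setting, and in 0% to two decimals in Set B. In Set A the mean shift was 1.4–2.3, 2.9–4.2 and 6.9–9.1 weeks at the three values of q, against a trial-to-trial SD of the median of 7–14 weeks. The curve moves even when the median does not: in Set B (9-month median, 24-month follow-up) the mean 12-month estimate was 0.493 against 0.474, 0.513 against 0.475, and 0.553 against 0.475.

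**5. Deaths among the censored.** Set A, mean dead over mean censored: 1.1/9.1, 0.9/12.7 and 0.8/15.2 at q = 5%; 2.2/10.1, 1.9/13.5 and 1.6/16.2 at 10%; 4.5/12.2, 3.7/15.2 and 3.1/17.6 at 20%. That is 5–12%, 10–22% and 18–37% of the responders reported as censored. The highest Set B values for 29 responders, at a 6-month median, were 2.9/7.5 (q = 10%) and 5.6/10.3 (q = 20%).

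**The case against.** The strongest reply is that nothing is broken. Five places in the two documents define DOR the same way, none requires death to be an event, and the endpoint is descriptive. That stands: this is a choice of estimand. It does not answer the reporting gap. rPFS and OS do include deaths, but neither is shown for responders.

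The effect may also be small. Scans continue after treatment stops until confirmed progression (protocol 5.1.4 and 9.6.3), which pushes q down. With scans on schedule the typical shift in the observed median is zero at q of 10% or less. This stands too, and q = 20% has no support in the documents.

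A single added count would cure the transparency problem, since SAP 3 sets a minimum output. That is partly right. The count is the cheapest remedy, but it gives no curve in which death ends the response.

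Finally, simply borrowing 10.2.2 would import its unclear censoring sentence. If only its handling of deaths were taken over, progression after new therapy could count while death after new therapy would not. That objection is correct, and the change below allows for it.

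A reader might infer more than the documents support:

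- **That DOR will be materially overstated in this trial.** This cannot be said without q; with no such deaths the two versions coincide. The curves can also cross briefly between a patient's last scan and his death, so the direction holds on average, not at every point.
- **That protocol and SAP conflict, or that the response-rate test is compromised.** They agree, and no decision rule uses DOR.
- **That PSA-DOR has the same fault.** Time to PSA progression (SAP 10.2.6) does not count death either, so the contrast with rPFS does not arise there.
- **That rPFS counts every death.** It does so only before new therapy and within the 24-week rule.

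**Conclusion.** The point holds as an estimand and reporting weakness. As written, radiographic DOR censors responders who die without documented progression, on average gives a longer duration than counting death, and does not show how many such deaths occurred.

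The size cannot be fixed from the documents. At assumed q of 5%, 10% and 20%, under constant independent hazards:

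- The underlying median is longer by 5%, 11% and 25%.
- With 29 responders and scans on schedule, and no deaths set aside for new therapy, the observed median is longer in roughly 20–25%, 33–48% and 58–77% of simulated trials. Scan windows raise these shares; excluding deaths after new therapy lowers them.
- About 1, 2 to 3, and 3 to 6 of the censored responders would be dead.

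These figures measure the gap between two estimands. They include nothing for informative censoring.

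**What to change.** 1. In SAP 10.2.1 and the radiographic part of the SAP Table 1 DOR row, define radiographic DOR as the time from first (later confirmed) response to radiographic progression or death from any cause, whichever comes first.
2. State that the 10.2.2 rules on subsequent anticancer therapy and the 24-week window apply to both scans and deaths in this analysis. At present 10.2.1 has no new-therapy rule, and protocol 5.1.4 continues scans after new therapy starts.
3. Align the 10.2.2 censoring sentence with its own definition, so that censoring applies only to patients with neither documented progression nor death.
4. Keep the progression-only DOR, which matches the protocol and Appendix 2, as supportive, and report the number of responders who died without documented progression.
5. Leave PSA-DOR unchanged.
6. Log the change in SAP Section 13, which already records changed definitions for PSA response and for clinical benefit rate: "The clinical benefit rate analysis in the protocol has been described in more detail in the SAP".

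The cost is wording in three places, one log entry, one supportive analysis and one extra count. Death dates are already collected for OS and rPFS, and no protocol amendment is needed. The reported DOR may be slightly shorter, and the SAP definition will then differ from the protocol's, as it already does for those two endpoints.

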10.2.2 Radiographic PFS

rPFS is defined as the time from first dose of rucaparib to the date of first objective evidence of radiographic progression (soft tissue or bone lesion) or death due to any cause, whichever occurs first, plus 1 day. Radiographic disease progression includes confirmed bone disease progression and soft tissue disease progression adjudicated by IRR using the PCWG3 guidelines for bone disease and modified RECIST Version 1.1 for soft tissue disease. Patients without a documented event of progression will be censored on the date of their last adequate tumor assessment (i.e., radiographic assessment) or date of first dose of study drug if no post-baseline tumor assessments have been performed.

Patients who withdraw from treatment prior to radiographic progression will be followed for disease status and survival whenever possible. Only tumor scans (and deaths, for PFS analyses) prior to start of any subsequent anticancer treatment will be included. If a patient discontinues study drug due to a reason other than radiographic PD and subsequently begins another anticancer therapy (ACT) prior to a PFS event, that patient will be censored at the last scan prior to the start of ACT. However, scans/PFS events occurring more than 24 weeks after DC/stop of study drug and more than 24 weeks after their last previous scan but prior to start of subsequent ACT will not be included in the analysis and such patients will be censored at their last scan prior to the end of the 24-week window.

rPFS will be presented by gene mutation for all patients (separately, using IRR and Investigator assessments) and may also be presented by measurable disease status at Baseline.

A sensitivity analysis will be performed in which patients who have discontinued without radiographic progression, but who have had PSA progression, will be treated as having an event at the time of PSA progression.

rPFS will be summarized using Kaplan-Meier methodology and in the case of a low censoring rate it may be summarized with descriptive statistics.

10.2.3 Overall Survival

OS is defined as the date from first dose of rucaparib to the date of death due to any cause, plus 1 day. OS will be summarized using the Safety Population, by gene mutation and Overall, using Kaplan-Meier methodology. OS may also be summarized for the subgroups of

patients defined by measurable disease status at baseline. In the case of a low censoring rate OS may be summarized with descriptive statistics.

10.2.4 Clinical Benefit Rate

Clinical benefit rate (CBR) is defined as the number of patients without radiographic progression (defined by modified RECIST Version 1.1/ PCWG3 criteria) who were continuing with study drug treatment through the given time interval divided by the number of patients who had the given amount of follow-up. Clinical benefit rates will be summarized at several intervals: e.g., 4-, 6-, 9-, and 12-months, with frequencies and percentages along with 95% confidence intervals. For example, the 6-month CBR would be the number of patients who neither discontinued nor had radiographic PD through 6 months divided by the number of patients who were enrolled at least 6 months prior to the visit cut-off.

CBR will be summarized for all patients (separately, using IRR and Investigator assessments) and may also be summarized for the subgroups of patients defined by measurable disease status at baseline.

10.2.5 Confirmed PSA Response

Confirmed PSA response ($\geq 50\%$ reduction) will be analyzed for all patients who had PSA values at baseline as described in [Section 10.1](#). Similarly, PSA response will also be analyzed using a $\geq 90\%$ reduction.

10.2.6 Time to PSA progression

Time to PSA progression is defined as the time from first dose of rucaparib to the date that a $\geq 25\%$ increase and absolute increase of ≥ 2 ng/mL above the nadir (or baseline if there was no PSA decline after baseline) in PSA was measured, plus 1 day. The increase must be confirmed by a second consecutive assessment conducted at least 3 weeks later (unless the PSA progression occurred at the last recorded PSA assessment). If confirmed, the date used for time of PSA progression is the earlier of the 2 PSA dates. Additionally, early rises (before 12 weeks following first dose of study drug) are not considered in determining PSA progression.

Time to PSA progression will be summarized for all patients and may also be summarized for the subgroups of patients defined by measurable disease status at baseline.

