9.5.5 Study Day 57 (Week 9) and Every 28 Days Thereafter

Patients will be instructed to refrain from taking their first dose of rucaparib at home on study visits when plasma samples are collected for PK.

Plasma samples for PK analysis should be collected before the morning dose on Study Day 57, Day 85, and Day 113 as close to 12 hours after the previous dose as possible. If the start of the next dose is delayed, the PK sample should still be collected during this visit instead of the delayed start of the next study visit;

The following procedures will be completed:

- PRO collected using the BPI-SF ([Appendix 6](#)), FACT-P ([Appendix 7](#)), EQ-5D-5L ([Appendix 8](#)), and analgesic drug score instruments ([Appendix 9](#); should be completed before other procedures)
- Physical examination
- Weight
- Vital signs
- Tumor assessment scans at the end of every 8 calendar weeks (± 7 days) for the first 24 weeks (Weeks 9, 17, 25), and then every 12 calendar weeks (± 7 days) thereafter (Weeks 37, 49, 61, etc)
- Concomitant medications and procedures
- ECOG performance status ([Appendix 3](#))
- PSA measurement
- Hematology

- Serum chemistry (fasting is not required)
- Urinalysis
- Plasma sample for ctDNA
- Plasma sample for PK analyses (Study Day 57, Day 85, and Day 113 only)
- AE (inclusive of SAE and AESI) monitoring
- Dispensation of rucaparib

Patients will ingest rucaparib twice daily at about the same times every day as close to 12 hours apart as possible. Rucaparib should be taken with at least 8 oz (240 mL) of water with or without food. Patients will keep all unused containers (empty, partially used, and/or unopened) and return with them to the study site for accountability at the next visit. In the event of toxicities, re-treatment or dose modification will be according to the criteria described in [Section 7.4.2](#).

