Time to PSA progression is defined as the time from first dose of rucaparib to the date that a $\geq 25\%$ increase and absolute increase of ≥ 2 ng/mL above the nadir (or baseline value for patients who did not have a decline in PSA) in PSA was measured. The increase must be confirmed by a second consecutive assessment conducted at least 3 weeks later.

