To assess time to PSA progression	Time from first dose of rucaparib to the date that a \geq 25% increase and absolute increase of \geq 2 ng/mL above the nadir is observed, confirmed by a consecutive measure at least 3 weeks later
To assess the safety and tolerability of rucaparib	The incidence of adverse events (AEs), clinical laboratory abnormalities, dose modifications, vital signs, ECGs, physical examinations, and ECOG performance status
To characterize the steady-state pharmacokinetics (PK) of rucaparib	Trough level plasma rucaparib concentrations (C_{min})

Exploratory Objectives	Exploratory Endpoints
To evaluate patient reported outcomes (PRO) using the EuroQol 5 dimensions questionnaire (EQ-5D-5L), Functional Assessment of Cancer Therapy – Prostate (FACT-P), analgesic drug score, and Brief Pain Inventory – Short Form (BPI-SF) instruments	Change and/or percent change from baseline for the EQ-5D-5L instrument. FACT-P and BPI-SF summarized according to their respective scoring manuals. Analgesic drug score recorded according to the World Health Organization (WHO) scale.
To assess changes in the molecular profile over time of matched pre- and post-treatment tumor and plasma samples	Changes in cancer-related mutations detected in plasma and tissue samples.
To assess concordance in HRR gene mutation status in matched screening biopsy tumor tissue, archival primary and metastatic tumor tissue and plasma ctDNA	Pairwise comparisons of available tissue and plasma HRR testing results.
To assess ctDNA as a molecular marker of response	Target lesion and/or PSA dynamics in relation to available longitudinal ctDNA test results.
To assess time to first subsequent antineoplastic therapy	Kaplan-Meier plot and/or descriptive statistics.
To evaluate loss of heterozygosity (LOH) in metastatic disease site biopsy and archival primary and metastatic tumor tissue samples	Concordance between percentage genomic loss of heterozygosity (%LOH) in available archival primary and metastatic tumor tissue samples.
To evaluate mechanisms of response and resistance in ctDNA and progression tumor tissue samples	Target lesion and/or PSA dynamics in relation to available plasma and tissue test results.

[figure not shown]

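### SAP 10.2.6 counts an unconfirmed PSA rise as progression when it is the last recorded value, even for patients still on rucaparib whose confirming PSA is not yet due

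*SAP*

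**What the plan says.** Protocol 11.5.2 defines PSA progression as a rise of at least 25% and at least 2 ng/mL above nadir (or above baseline if PSA never fell), and adds: "The increase must be confirmed by a second consecutive assessment conducted at least 3 weeks later". SAP Table 1 (Section 2.1) gives the same thresholds and requires that the rise be "confirmed by a consecutive measure at least 3 weeks later". Neither has an exception.

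SAP 10.2.6 keeps the thresholds and the confirmation rule but waives confirmation "unless the PSA progression occurred at the last recorded PSA assessment". It sets no condition on treatment status or on why no later value exists. Two limits do apply: both thresholds must be met, and "early rises (before 12 weeks following first dose of study drug) are not considered in determining PSA progression". The event date is given for one case only: "If confirmed, the date used for time of PSA progression is the earlier of the 2 PSA dates". No date is given for an unconfirmed last rise. Section 10.2.6 also states no censoring rule, although SAP 11.1 says such rules are described under each endpoint.

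SAP Section 13 shows the protocol text and the new text together. It explains the change by saying that the protocol definition "did not contain all the details outlined in the PCWG3 guidelines".

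**The concern.** A patient on rucaparib has a PSA at "Study Day 57 (Week 9) and Every 28 Days Thereafter" (Protocol 9.5.5). SAP 10.2.4 foresees analysis at a visit cut-off, and under Protocol 5.3 the study closes only after all patients have discontinued. At any earlier cut-off, some patients can therefore still be on treatment. For them, the last recorded PSA is last only because the cut-off came before the next visit. The same isolated rise one visit earlier, followed by a value back below threshold, would not be an event. Event status then depends on where the cut-off falls, and an event counted at one cut-off can vanish at the next.

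The definition has three uses that matter here. It is the event for time to PSA progression (10.2.6). It ends PSA duration of response (10.2.1). It also enters the Cohort B primary endpoint, because SAP 10.1 requires both values of a confirmed PSA response to precede PSA progression as defined in 10.2.6.

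**Working it through.** The plan states no sample size, power or event count for time to PSA progression, so there is no figure of its own to reproduce. The Cohort B two-stage designs, which use PSA response, do reproduce. Reject if responses in stage 1 exceed the futility bound and the total reaches the target: 4/19 then 16/54 gives type I error 0.048 and power 0.904; 4/18 then 11/33 gives 0.046 and 0.801. These calculations do not involve the exception.

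**Step 1: who is affected.** A patient still on treatment at a cut-off before closure, with a last PSA at week 12 or later, at least 25% and at least 2 ng/mL above nadir, and no later value. Under Protocol 11.5.2 and Table 1 this is not an event. Under 10.2.6 it is.

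**Step 2: the Cohort B route.** Take baseline 100 ng/mL, then 80 (Day 29), 60 (Day 57), 20 (Day 85) and 30 (Day 113, last recorded).
- 20 and 30 are consecutive, 28 days apart, and both at or below 50% of baseline.
- Against the nadir of 20, the value 30 is a rise of 10 ng/mL, or 10/20 = 50%, so it qualifies as an unconfirmed last rise.
- Progression then falls on Day 113, the second response value does not precede it, and the responder is lost on a literal reading.
- If the next PSA is 22, the rise is not confirmed and the patient becomes a responder. If it is 30 again, progression is confirmed and dated Day 113, so the response fails either way. The exception changes the result only where the next value would not have confirmed.

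**Step 3: size, as an illustration.** The documents give no within-patient PSA coefficient of variation (CV), so it is assumed. Model: true PSA constant at 20 ng/mL after the initial fall; independent lognormal readings every 28 days from Day 29; Day 29 and Day 57 count towards the nadir but cannot be events; 200,000 patients per cell. A confirmed false event needs two consecutive readings at least 1.25 times, and at least 2 ng/mL above, the nadir before the first of them. The added share is the proportion of all flat-PSA patients with no confirmed event whose final reading alone meets both thresholds.

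| Assumed CV | Already falsely confirmed, 6 / 12 readings | Added by the exception, 6 / 12 readings |
|---|---|---|
| 5% | 0.0% / 0.2% | 0.3% / 0.7% |
| 8% | 3.0% / 12.9% | 7.1% / 9.4% |
| 10% | 8.9% / 32.2% | 12.7% / 12.8% |
| 15% | 27.4% / 69.9% | 19.5% / 9.7% |
| 20% | 41.6% / 85.9% | 20.4% / 5.9% |

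**Step 4: the 2 ng/mL floor.** A 25% rise equals 2 ng/mL at a nadir of 2/0.25 = 8 ng/mL. Below that, the floor is the stricter test: from a nadir of 4 the rise must be 2/4 = 50%. With 12 readings, the added share at CV 10% / 15% is 1.7% / about 10% at a true level of 5 ng/mL, 0.0% / under 1% at 3 ng/mL, and 0.0% / 0.0% at 2 ng/mL.

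**The case against.** The exception has a legitimate use. Protocol 9.6.1 lists a PSA at the Treatment Discontinuation Visit, but 9.6.2 and 9.6.3 list none at the 28-Day Follow-up or in long-term follow-up, so a rise at discontinuation may never be confirmable. Section 13 also discloses the change and attributes it to PCWG3 details. Both points stand. They justify an exception for patients off treatment, but not one that also covers patients with a PSA still to come. Nor does disclosure remove the conflict with Table 1.

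The endpoints directly affected are secondary and descriptive in a single-arm study, and the bias shortens durations, so it does not favour the drug. The simulation contains no patient whose PSA is truly rising. In practice some last-value rises are real, and censoring them would lengthen the estimates. These points stand and limit the weight of the finding.

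Four stronger readings are tempting but not supported:
- **The rPFS sensitivity analysis is distorted too.** SAP 10.2.2 counts PSA progression there only for patients who have discontinued without radiographic progression, so an on-treatment patient cannot become an event.
- **Responders with low PSA are hit hardest.** The 2 ng/mL floor largely protects them (Step 4).
- **At CV 15-20%, about 27-41% of flat-PSA patients are wrongly ended.** Those are shares of patients without confirmed progression, a group that shrinks as readings accumulate. At 12 readings and CV 15%, 9.7/(100 - 69.9) is about 32% of the remainder but 9.7% of all. At CV 20%, 86% are already falsely confirmed, which is a weakness of the confirmation rule itself.
- **Any last-value rise becomes an event.** Only rises from week 12 that meet both thresholds do.

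**Conclusion.** The point holds. The exception in SAP 10.2.6 is wider than its justification and conflicts with Protocol 11.5.2 and SAP Table 1. At a cut-off before closure it makes the event status of some on-treatment patients depend on the cut-off date. It shortens time to PSA progression and PSA duration of response and, read literally, can remove a Cohort B responder.

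The size rests on an assumed CV, a flat true PSA and independent readings. Over CV 5-20% and 6 to 12 readings, the exception adds false events in between under 1% and about 20% of flat-PSA patients at 20 ng/mL. These are shares of such patients, not of the trial population. The change is worth making because the rule is easily corrected and touches a primary endpoint, but it does not threaten the trial's main conclusions or the Cohort B design calculations.

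**What to change.** In SAP 10.2.6, limit the exception to patients who have permanently stopped rucaparib and have no further PSA scheduled, and state the event date for that case. For patients still on treatment at the cut-off, censor an unconfirmed last rise at that assessment, for both time to PSA progression and PSA duration of response. State the general censoring rule for time to PSA progression, which 10.2.6 now lacks. In 10.1, say that an unconfirmed last rise in an on-treatment patient does not cancel a confirmed PSA response. Align Table 1, 10.2.6 and Section 13. No change to the rPFS sensitivity analysis is needed.

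The cost is a few sentences and one programming condition on treatment status at the cut-off. The downside is more censoring at an early cut-off, including some true rises not yet confirmed. Reporting the current rule as a sensitivity analysis would show how much this matters.
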